### Protocol Synopsis

Title	A Prospective Multicenter Pilot Study of the SPR™ System for the Treatment of Post-Stroke Shoulder Pain
Indication	The SPR System is intended for the reduction of post-stroke shoulder pain for patients who are unresponsive to or cannot tolerate conventional therapy (medications, slings, etc.)
Investigational (Test) Device	The SPR™ ( Stimulation for Pain Relief ) System
Study Design	Prospective Multicenter Case Series Study
Primary Study Objective	To gather preliminary data on the safety, clinical efficacy, and performance of the SPR System for the treatment of post-stroke shoulder pain.
Study Plan	
Subjects with chronic (<math>\geq</math> 6 months) post-stroke shoulder pain rated as <math>\geq</math> 4 on the Brief Pain Inventory pain intensity question (Question #3) will receive the first stage of the SPR System. The SPR System is a two-staged neurostimulation therapy which delivers stimulation to the [REDACTED] shoulder. The first stage (SPR Trial Stage) uses a temporary [REDACTED] Lead placed percutaneously [REDACTED] and a body-worn external stimulator (the Smartpatch Stimulator). Subjects meeting the specified success criteria at the conclusion of the SPR Trial Stage who then experience a return of pain within 6 months of completion of the Trial Stage will be consented and screened for eligibility for the second stage (SPR Implant Stage). A "return of pain" is defined as: 1) an increase in pain by at least 2 points compared to the end of Trial Stage (Visit 5) pain score; and 2) BPI Question #3 score of at least 4 (both criteria must be met for at least 2 weeks). The SPR Implant Stage uses an Implantable Pulse Generator (IPG) and an Implantable [REDACTED] Lead.
 
Subjects will be permitted to continue use of non-opioid analgesic medications throughout the study; however, dosages of these medications will be controlled during the study. Subjects will be permitted to reduce or maintain their dosage of non-opioid analgesic medications, however, they will be asked to not increase their dosage of these medications above their baseline dosage during the week prior to each study visit and scheduled telephone call (and during the six month Trial Stage follow-up period). Subjects will not be permitted to continue use of opioid analgesic medications (except as needed in the week immediately following the Implant Stage procedure for post-surgical pain management), to receive injections to the affected limb, or to use slings or other stabilization devices/methods during study participation. Subjects who require concurrent physical or occupational therapy for shoulder pain will be excluded.
 
Subjects will use the Smartpatch System for 6-weeks during the Trial Stage. To evaluate the placebo effect, the first 3-weeks of the SPR Trial Stage consist of a sham period in which the SPR Trial Stage system (i.e., the Smartpatch System) is placed, but stimulation is not delivered. Subjects will be blinded to the fact that stimulation is not being delivered. Following the sham period, stimulation will be turned on, and subjects will receive stimulation for a total of 6 hours per day for 3 weeks. Subjects will be queried for pain intensity on a weekly basis during the SPR Trial Stage using the BPI Short Form Question #3 (BPI3), and subjects will be instructed to focus on their shoulder pain when answering the BPI. At the end of the sham period, pain intensity will be compared to baseline pain intensity scores to evaluate the effect of sham stimulation. At the conclusion of the SPR Trial Stage, subjects achieving at least a 2-point reduction on the BPI3 will be Trial Stage successes. These subjects will receive monthly follow-up calls in order to determine eligibility to advance to the SPR Implant Stage. During the


	
Implant Stage, subjects will receive the fully implantable SPR Implant Stage system and be followed for 3 years.
 
All primary and secondary endpoints will be assessed at baseline and again at the completion of the sham period and the active stimulation period of the SPR Trial Stage. In addition, primary endpoints will be evaluated via monthly phone calls during the Trial Stage follow-up period as well as at visits during the SPR Implant Stage (3-weeks, 6-weeks, 12-weeks, 6-months, 9-months, and 12-months post IPG Stim ON). In addition, long-term follow-up will be conducted on an annual basis at 24-months and 36-months post IPG Stim ON.
 
Primary efficacy of the Trial Stage will be determined at the end of the Trial Stage. Primary efficacy of the Implant Stage will be determined at 12-weeks post IPG Stim ON. All Implant Stage subjects will continue to be evaluated at 6, 9, and 12-months post IPG Stim ON follow-up visits and annually for 36 months to determine the long-term efficacy and safety profile of the SPR Implant System and to evaluate the effect of dosage (number of hours of use each day) on treatment effect. Adverse events will be assessed at all follow-up visits.

Number of Sites	Up to 5 Investigational Sites will be enrolled
Number of Subjects	45 subjects will participate in the SPR Trial Stage. Although we expect to yield approximately 18 subjects with an implantable system (SPR Implant Stage), all eligible Implant Stage subjects will be permitted to advance to the Implant Stage.
Inclusion Criteria	
 
• At least 21 years old
 
• <math>\geq 6</math> months after the stroke that caused shoulder pain
 
• Subject failed or did not tolerate at least two conservative therapies for a total period of at least 6 months since the onset of post-stroke shoulder pain.
 
• Shoulder pain as indicated by a score of <math>\geq 4</math> on the Brief Pain Inventory Short Form Question 3 (BPI3)
 
• Upper extremity hemiplegia (no shoulder abduction, shoulder abduction in synergy, or if isolated movement is present, Medical Research Council (MRC) grade <math>\leq 4/5</math>)
 
• Cognitive ability to fulfill study requirements based upon a score of <math>\geq 24</math> on the Mini Mental Status Exam (MMSE)
 
• Ability to appropriately rank pain on a Numeric Rating Scale (based upon the Investigator's determination of the subject's ability to rank pain)
 
• Availability of a reliable adult who can check the skin and assist the subject with the study protocol requirements
 
• Able and willing to take part in study and comply with all study requirements
 

Additional Inclusion Criterion for Implant Stage	
In addition to continuing to meet the above inclusion criteria (with the necessary pain score already having been confirmed at a Trial Stage Follow-up Call), subjects must:
 
 
• Be a Trial Stage Success AND
 
• Have a clinically significant return of pain as defined by an increase in BPI3 score of at least 2 points (compared against the BPI3 score at Visit 5) resulting in a BPI 3 score of at least 4 within 6 months of the end of the Trial Stage that is sustained for at least two consecutive weeks.
 

Exclusion Criteria	
 
• Evidence of joint or overlying skin infection of the affected limb
 
• Taking opioid medication (or Tramadol) for shoulder pain OR for any other chronic pain condition
 

	
 
• Intra-articular or sub-acromial steroid injections or botulinum toxin injections to the affected shoulder in the previous 12 weeks
 
• History of arrhythmia with hemodynamic instability, such as ventricular tachycardia, supraventricular tachycardia and rapid ventricular response atrial fibrillation OR valvular heart disease including artificial valves
 
• Evidence of non-stroke related shoulder pathology with continuing symptoms (such as pathology related to a traumatic injury, tumor, or infection)
 
• Bleeding disorder OR INR >3.0 for those on warfarin
 
• Unable, per the prescribing physician, to stop antiplatelet medications [e.g., aspirin, clopidogrel (Plavix)] and/or anticoagulants for at least 7 days prior to SPR implantation
 
• Receiving outpatient physical or occupational therapy for shoulder pain
 
• History of recurrent skin infections
 
• Compromised immune system based upon medical history (i.e., HIV/AIDS, actively taking or recently completed immunosuppressive therapies such as chemotherapy or radiation of the head/neck, congenital immunodeficiency, or any other cause for compromised immune system documented in the medical history)
 
• Any other medical condition that may interfere with ability to participate in a clinical trial as determined by the Investigator
 
• Severely impaired communication skills (receptive or expressive) as determined by the Investigator
 
• Confounding conditions such as ipsilateral upper limb lower motor neuron lesion, Parkinson's Disease, SCI, traumatic brain injury, MS, or complex regional pain syndrome
 
• Uncontrolled seizures (>1 per month for 6 months)
 
• An implanted electronic device
 
• Allergy to skin surface electrodes and/or medical-grade adhesive tapes
 
• Allergy to local anesthetic agents such as lidocaine or previous reaction to Monitored Anesthesia Care (MAC)
 
• Pregnant
 
• Prisoners, minors, legally incompetent people, unconscious patients, house staff, or students
 

Primary Safety Endpoint	
 
• Occurrence of device-related adverse events.
 

Primary Clinical Endpoint	
 
• Trial Stage Success 
 
◦ Statistically significant proportion of subjects achieving at least a 2-point reduction in post-stroke shoulder pain intensity score in the BPI Pain Intensity Question #3 (BPI3) at the end of the Trial Stage (Visit 5) relative to end of the placebo period or baseline (Visit 4 or Visit 1), whichever is lower OR reporting a BPI3 score of zero at the end of the Trial Stage.
 
 
 
• Implant Stage Success 
 
◦ Statistically significant proportion of subjects participating in the Implant Stage achieving at least a 2-point reduction in post-stroke shoulder pain intensity score in the BPI Pain Intensity Question #3 (BPI3) at the 12-week post-IPG stim on visit (Visit 10) relative to end of the placebo period or baseline (Visit 4 or Visit 1), whichever
 
 
 

	is lower OR reporting a BPI3 score of zero at the 12-week post-IPG stim on visit.
Secondary Endpoints	
 
• Pain 
 
◦ BPI Pain Interference Question (BPI9)
 
◦ Pain-free passive range of motion
 
 
 
• Quality of Life 
 
◦ Medical Outcomes Study Short Form (SF-36v2)
 
 
 
• Global impact of stimulation therapy 
 
◦ Patient Global Impression of Change (PGIC) scale
 
 
 
• Emotional functioning 
 
◦ Beck Depression Inventory Second Edition (BDI-II)
 
 
 
• Device Performance and User Satisfaction of SPR System
 
• Changes in Quantitative Sensory Testing (QST) thresholds
 
• Impact of Therapy on Arm Impairment using the Stroke Upper Limb Capacity Scale (SULCS)
 
• Economic Impact of Shoulder Pain at Baseline
 

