As a safety precaution to prevent potential excessive bleeding, subjects on warfarin will have blood drawn to confirm an INR of  $<3.0$ . If the INR is not below 3.0, subjects will be given the opportunity to have their warfarin dosage adjusted and the INR will be retested up to two additional times. The INR must be collected within 48 hours prior to the SPR Trial Stage procedure. In addition, a pregnancy test will be conducted in females of reproductive potential.

Once a subject has met all eligibility criteria, the Subject ID will be assigned.

During this visit, subjects will also be assessed for Pain-Free Range of Motion, complete the SF-36v2, complete the BDI-II, and be provided with an Economic

Impact Survey for completion at home. The SULCS and the QST testing (optional) will also be completed at this visit for subjects enrolled following the integration of these tests into the protocol.

Information regarding baseline pain medications (including type, dosage, and frequency) will be collected from the subject and/or their caregiver during this visit. Medications will be categorized as to whether they are used to treat shoulder pain or other types of pain. Subjects will be asked to control these pain medications. They will be instructed that dosages of pain medications should be maintained or can be decreased from their baseline dosage during the week prior to each study visit and phone call for the duration of their study participation. Thus, subjects will be asked to not increase their medication dosages above their baseline dosage during the week prior to each study visit and phone call for the duration of their study participation. The 1-week period was selected because the primary endpoint, BPI pain intensity, asks subjects to recall their worst pain in the past week.

Due to the frequency of visits during the Trial Stage, this medication protocol asks subjects to maintain or decrease their dosages throughout the duration of the Trial Stage. For pain medications that are taken on an as needed basis (e.g. "PRN"), subjects will be queried at baseline for their highest "as needed dose". Future "as needed" dosages during the week prior to the study visits and phone calls should not exceed this dosage.

If pain medication for breakthrough shoulder pain or other types of pain is required beyond their baseline dosage, this will be documented and analyzed in accordance with Sections 6.1 and 6.2.

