##### **6.1.2.2 SPR Trial Stage Success**

Trial Stage success for each subject is the binary outcome pertaining to success (a 2-point or greater decrease in BPI3 during the Trial Stage or failure (a decrease of less than two points, no change in BPI3, or increase of BPI3 during the Trial Stage). BPI3 at the end of the Trial Stage (Visit 5) will be compared to BPI3 at the End of Sham (Visit 4) for subjects who demonstrate either no placebo or a positive placebo effect. For subjects in whom a negative placebo effect was observed, BPI3 results at Visit 5 will be compared against Baseline (Visit 1).

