This interim analysis will also include an examination of mean changes in the normalized dose of nonopioid medications using pain medication data collected at baseline from the subject (including type, dosage, frequency, and whether the medication is used to treat shoulder pain or other types of pain) compared against each subsequent visit. The analysis will be used to confirm that pain medication dosages did not increase for the week prior to each visit and call and during the Trial Stage follow-up period, in accordance with the study protocol. Although subjects will be asked to maintain pain medication dosages, an increase in dosage for breakthrough pain is permitted. For this pilot study, there is no limit on the number of pain medication uses for breakthrough shoulder pain or other types of pain. The number of uses of breakthrough medication will be analyzed for each subject. Further analysis of this data will be used to evaluate the need for limits on rescue medications for breakthrough pain during the future pivotal study on the implantable system.

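### Analgesic dose is capped and checked against Baseline, but success is mostly scored from End of Sham, so a dose rise over the scored interval can go unreported

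*Combined protocol and SAP*

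**What the plan says.** **Ceiling.** The Synopsis (Study Plan) states: "Subjects will be permitted to reduce or maintain their dosage of non-opioid analgesic medications". It then sets the limit: "they will be asked to not increase their dosage of these medications above their baseline dosage during the week prior to each study visit" or scheduled call. Section 4.1 repeats this, and Section 4.5.2.10 applies the same limit throughout the follow-up calls. No section makes a reduced dose the new ceiling.

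**As-needed drugs.** Under Section 4.5.1, "subjects will be queried at baseline for their highest" as-needed dose, and later as-needed "dosages during the week prior to the study visits and phone calls should not exceed this dosage". The limit is a recorded maximum, not what was taken in the Baseline week.

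**Trial Stage wording.** Section 4.5.1 adds that "this medication protocol asks subjects to maintain or decrease their dosages throughout the duration of the Trial Stage".

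**Dose check.** Section 6.1.2.4 plans an "examination of mean changes in the normalized dose of nonopioid medications using pain medication data collected at baseline from the subject", which includes "whether the medication is used to treat shoulder pain or other types of pain) compared against each subsequent visit". Its stated aim is to confirm that doses did not increase. Section 6.2 repeats the analysis at 36 months.

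**Scoring.** Section 6.1.2.2 states: "BPI3 at the end of the Trial Stage (Visit 5) will be compared to BPI3 at the End of Sham (Visit 4"), for subjects with a positive or no placebo effect. Baseline is the reference only if pain rose during sham. Sections 5.4.1.4 and 6.1.2.3 use the same references for Visit 10. No success definition mentions medication.

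**The concern.** The pain contrast starts at Visit 4 for two of the three rows of Table 9, while the dose contrast starts at Visit 1 for everyone. The check is meant to rule out an analgesic explanation, but it is not aimed at the interval over which success is scored. Dose can be lower at Visit 4 than at Visit 5 or Visit 10, never exceed the ceiling, and show no change from Baseline at the endpoint.

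Section 5.4.1.2 explains its reference rule as a way to credit stimulation rather than placebo. Without a concurrent control group, nothing else in the design separates analgesic relief from device relief over that interval. Trial Stage success is also one of the conditions for Implant Stage screening.

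**Working it through.** The plan gives no figure to reproduce: the null rate is redacted, and no analgesic effect or prevalence is stated. The check is therefore of the rules, followed by an illustration under assumptions.

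**Step 1. The rule.** Let P0, P1 and P2 be BPI3 at Visits 1, 4 and 5. Success means min(P0, P1) − P2 ≥ 2, or P2 = 0 (Synopsis, Primary Clinical Endpoint). For Visit 10, replace P2 by P4.

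**Step 2. Fixed-dose user, no stimulation effect, no noise.** Let s be the sham or natural improvement and m the pain relief lost on the lower Visit 4 dose and regained later.
- P1 = P0 − s + m and P2 = P0 − s, so the fall from the reference is min(s, m).
- P0 = 7, s = 2, m = 2: P1 = 7, P2 = 5, fall 2. This is a success with zero dose change from Baseline.
- P0 = 7, s = 1, m = 2: P1 = 8, so the reference reverts to 7; P2 = 6, fall 1. Not a success.
- If the Visit 4 dose is kept, P2 = P1 and the fall is never positive. With P0 = 7 and s and m each from 0 to 4, there are no successes.

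**Step 3. As-needed user below the recorded maximum at Visits 1 and 4, at the maximum before Visit 5.** With s = 0, P0 = P1 = 7 and P2 = 7 − m. Any m ≥ 2 is a success, because both possible reference scores come from low-use weeks. If the Baseline dose is entered as the recorded maximum, the check again shows no increase.

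**Step 4. Illustration with noise.** Assumed: mean pain 7, between-subject SD 1.5, visit noise SD 0.7 to 1.5, integer scores from 0 to 10, entry at P0 ≥ 4, m = 1 or 2, zero stimulation effect, 400,000 simulated subjects per setting, Visit 5 endpoint. If 20% of subjects follow the pattern, the rise in the success rate is 0.20 × (rate with dose restored − rate at constant dose).

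| Fixed-dose pattern | Constant dose | Cut, then restored | Rise at 20% prevalence |
|---|---|---|---|
| s = 0 | 2–12% | 5–20% | 0.6–1.7 points |
| s = 1 or 2 | 5–21% | 17–55% | 1.7–9.5 points |

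- Smallest: s = 0, SD 0.7, m = 1 gives 0.20 × (5.2 − 2.2) = 0.6.
- Largest: s = 2, SD 0.7, m = 2 gives 0.20 × (54.6 − 7.0) = 9.5.
- For the as-needed pattern of Step 3 with s = 0, success is 17–55% against 2–12% at constant dose.

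**Step 5. In subjects.** With N = 45, 0.6 points is 0.006 × 45 = 0.3 subjects, 1.7 points is 0.8 and 9.5 points is 4.3. One false success adds 1/45 = 2.2 points in the Trial Stage and 1/18 = 5.6 points in the Implant Stage.

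**Step 6. Effect on the test.** Assume an exact one-sided test at 0.025 with N = 45 and null rates of 0.3 to 0.7. The actual error is 0.012–0.022. If a share c of true non-successes converts, the success rate becomes p + (1 − p)c, and the error becomes 0.033–0.046 at c = 5% and 0.054–0.118 at c = 10%. The top corner of Step 4 corresponds to c ≈ 9.5/93.0 = 10%; most settings give less.

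**The case against.** **A dose rise is not itself a success.** A reader might infer that any return to the Baseline dose counts as stimulation success. The rule does not work that way. BPI3 must fall at least 2 points below the lower of Visits 1 and 4, or reach 0. Step 2 shows that a fixed-dose user also needs sham or natural improvement, or favourable noise. This protection stands, but it is partial, and the as-needed user of Step 3 lacks it.

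**The check is not blind.** A reader might infer that it could never reveal a rise from Visit 4. Mean changes from Baseline are planned at every later visit, so widespread cutting and restoring would show as a negative mean at Visit 4 and about zero at Visit 5, and the rise follows by subtraction. That is correct for group means. It does not identify which subjects rose or whether they were the successes, and the stated purpose would not flag it.

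**The rise may not be permitted.** The Trial Stage sentence in Section 4.5.1 can be read as barring any rise after a cut. The sentences around it define the limit as the Baseline dose, so the text is open to both readings. It does not extend to Visit 10.

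**The direction is not fixed.** A subject may also take less at Visit 5 than at Visit 4, which works against the device. This stands: the net direction is unknown.

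**It is a pilot.** Section 6.1.2.4 already counts breakthrough use per subject and leaves rescue limits to the pivotal study. That lowers the stakes, but those counts are not linked to success and do not cover a rise that stays within the Baseline dose.

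**Conclusion.** The mismatch is in the text. The ceiling and the only planned dose analysis refer to Baseline, success is mostly scored from End of Sham, and no planned analysis compares a subject's endpoint dose with the dose at the visit that supplied the reference score. "Mostly" describes the rule (two of three rows in Table 9); the share of subjects is not given.

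The documents do not show that such rises happen or that results will be materially biased. The fixed-dose ranges of 0.6–1.7 and 1.7–9.5 points depend entirely on the assumed 20% prevalence, analgesic worth, noise and sham improvement, and 9.5 is the most extreme setting tried. They describe the Trial Stage population. Implant Stage subjects are a selected group, for whom only the structure of the argument carries over.

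This is a modest, inexpensive improvement to the medication analysis, not a flaw that invalidates the primary endpoint.

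**What to change.** In the medication analysis of Sections 6.1.2.4 and 6.2:
1. Compute each subject's normalized dose change in non-opioid analgesics taken for shoulder pain, from the visit that supplied the reference BPI3 (Visit 4, or Visit 1 for a negative placebo effect) to Visit 5 and to Visit 10. For as-needed drugs, use the amount taken in the recall week where recorded, not the permitted maximum.
2. Report how many subjects, and how many successes, had a higher dose at the endpoint than at the reference visit.
3. Repeat both success rates in a sensitivity analysis that counts those subjects as non-successes.

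Separately, the sponsor should reconcile the Trial Stage sentence in Section 4.5.1 with the Baseline ceiling in the Synopsis and Section 4.1. Which reading applies is for the sponsor to decide; the analysis is needed under either.

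Cost: SAP wording and a little programming. Medication use is already queried at Visits 4, 5 and 10 (Sections 4.5.2.5, 4.5.2.8 and 4.5.3.8), and Section 4.5.1 already classes drugs as for shoulder pain or other pain. The sensitivity rate may come out somewhat lower. It is conservative, because it also reclassifies genuine responders with a small rise, which is why it should not replace the primary definition.
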